6.0 Registration/Randomization Procedures

6.1 Registration Procedures

- 6.11 To register a patient, fax (██████████) a completed eligibility checklist to the Academic and Community Cancer Research United (ACCRU) Registration Office between 8 a.m. and 4:30 p.m. central time Monday through Friday.

NOTE: ACCRU-GI-1611 (COLOMATE) treating physician will provide COLOMATE Companion Trial Recommendation Form which will include the Patient ID that must be used for this study.

6.12 Correlative Research

Mandatory

A mandatory correlative research component is part of this study. The patient will be automatically registered onto this component (see Sections 3.0, 14.0 and 17.0).

Optional

An optional correlative research component is part of this study. There will be an option to select if the patient is to be registered onto this component (see Section 14.0).

- Patient has/has not given permission to give his/her blood sample for research testing.

6.13 Documentation of IRB approval must be on file in the Registration Office before an investigator may register any patients. Approvals should be uploaded using the online ACCRU Regulatory Management System (ARMS).

In addition to submitting initial IRB approval documents, ongoing IRB approval documentation must be on file (no less than annually) with ACCRU. Approvals should be uploaded using the online ACCRU Regulatory Management System (ARMS). If the necessary documentation is not submitted in advance of attempting patient registration, the randomization will not be accepted and the patient may not be enrolled in the protocol until the situation is resolved.

Submission of annual IRB approvals is required until the study has been closed through your IRB.

- 6.14 Prior to accepting the registration/randomization, the registration/randomization application will verify the following:
 - IRB approval at the registering institution
 - Patient eligibility
 - Existence of a signed consent form
 - Existence of a signed authorization for use and disclosure of protected health information
- 6.15 At the time of registration, the following will be recorded:
 - Patient has/not given permission to store and use his/her blood sample(s) for future research to learn about, prevent, or treat cancer.
 - Patient has/not given permission to store and use his/her blood sample(s) for future research to learn, prevent, or treat other health problems (for example: diabetes, Alzheimer's disease, or heart disease).
 - Patient has/not given permission to store and use his/her tissue sample(s) for future research to learn about, prevent, or treat cancer.
 - Patient has/not given permission to store and use his/her tissue sample(s) for future research to learn, prevent, or treat other health problems (for example: diabetes, Alzheimer's disease, or heart disease).
 - Patient has/not given permission for ACCRU to give his/her sample(s) to outside researchers.
- 6.16 Treatment cannot begin prior to randomization and must begin \leq 7 days after randomization.
- 6.17 Pretreatment tests/procedures (see Section 4.0) must be completed within the guidelines specified on the test schedule.
- 6.18 All required baseline symptoms (see Section 10.52) must be documented and graded.
- 6.19a Treatment on this protocol must commence at an ACCRU institution under the supervision of a medical oncologist.
- 6.19b Study drug is available on site.
- 6.19c Blood draw kit is available on site.

Exclusion: Guardant 360 kit does not need to be on site at the time of registration.

- 6.19d Patient questionnaire booklet is available on site; copies are not acceptable for this submission.

6.2 Randomization Procedures

- 6.21 The factors defined in Section 5.0, together with the registering membership, will be used as stratification factors.
- 6.22 After the patient has been registered into the study, the values of the stratification factors will be recorded, and the patient will be assigned to

one of the following treatment groups using the Pocock and Simon [39] dynamic allocation procedure which balances the marginal distributions of the stratification factors between the treatment groups.

- Panitumumab
- Standard Therapy (regorafenib or TAS-102)

7.0 Protocol Treatment

7.1 Treatment Schedule - Use actual weight or estimated dry weight if fluid retention

Arm	Agent	Dose Level	Route	Day	ReRx
A	Panitumumab	6 mg/kg	IV	Day 1 Day 15	Every 28 Days
B	TAS-102	35 mg/m ² (max 80 mg/dose)	Oral	Twice daily, days 1-5 and days 8-12	Every 28 Days
	Regorafenib	160 mg (alternative dosing permitted minimum 80 mg and max 160 mg)	Oral	Once daily, days 1-21	Every 28 Days

7.11 Arm A: Patients assigned to Arm A will receive panitumumab.

7.12 Arm B: Patients assigned to Arm B will receive either TAS-102 or regorafenib per treating physician discretion and will be dosed as per prescribing guidelines and at investigator discretion. Patients who have received TAS-102 prior to registration may only receive regorafenib. Patients who have received regorafenib prior to registration may only receive TAS-102. Patients cannot switch between TAS-102 and regorafenib during protocol treatment.

7.2 Patients can be instructed in administration techniques and granted treatment independence with nursing staff approval.

7.3 For this protocol, the patient must return to the consenting ACCRU institution for evaluation as per the study calendar during treatment. Additional visits during treatment are not mandated by the study protocol, but are advised to optimize symptom management and provide optimal care.

7.4 Treatment by a local medical doctor (LMD) is not allowed

7.5 Study treatment with panitumumab may be administered up to 3 days before or after the scheduled Day 1, Day 15 of each cycle due to administrative reasons.

8.0 Dosage Modification Based on Adverse Events

Subjects will be monitored continuously for AEs from the date of first dose of study drug and for 30 days after the last dose of study drug. Subjects will be instructed to notify their treating physician of any and all AEs. All AEs should also be managed with supportive care at the earliest signs of toxicity. Subjects should receive appropriate supportive care measures as deemed necessary by the Investigator. Suggested supportive care measures for the management of adverse events are outlined in Section 9.0.

Subjects experiencing one or more AEs due to study drug(s) may require dose modification(s) as described in Sections 8.1, 8.2, and 8.3. If multiple adverse events are seen, administer dose based on greatest reduction required for any single adverse event observed. Reductions or increases apply to treatment given in the preceding cycle and are based on adverse events observed since the prior dose. At the discretion of the Investigator, dose modifications are permitted outside of those provided in the protocol if the Investigator feels it is in the interest of the subject's safety (e.g., due to multiple toxicities, persistent toxicities, intercurrent illness, or short term compliance or monitoring issues, etc.). Subjects may need to be followed at least weekly when the study drug is held for clinically significant toxicity until the toxicity returns to Grade ≤ 1 or is determined to be controlled, chronic, or irreversible.

Dosing interruptions are permitted in the case of medical / surgical events or logistical reasons not related to study therapy (e.g., elective surgery, unrelated medical events, patient vacation, and/or holidays). Subjects should be placed back on study therapy within 4 weeks of the scheduled interruption, unless otherwise discussed with the Lead PI. The reason for interruption should be documented in the patient's study record.

ALERT: ADR reporting may be required for some adverse events (See Section 10)

8.1 Panitumumab: This section applies to adverse events associated with panitumumab. For adverse events associated with regorafenib, please refer to Section 8.2 and for TAS-102, please refer to Section 8.3.

* Located at [REDACTED]

** Use the following to describe actions in the Action column:

- Omit = Treatment is not given for this cycle
- Hold/Delay = Treatment can be made up as part of this cycle
- Discontinue = Treatment is totally stopped
- **Dose Modifications – Dermatologic Toxicity**

➤ **Table 8.11. Dose Modifications during Vectibix Treatment**

Occurrence of Skin Symptom(s): \geq grade 3 ^a	Administration of Vectibix	Outcome	Dose Regulation
Initial occurrence	Stop 1 or 2 doses	Improved (< grade 3)	Continue infusion at 100% of original dose
		Not recovered	Discontinue
At the second occurrence	Stop 1 or 2 doses	Improved (< grade 3)	Continue infusion at 80% of original dose

		Not recovered	Discontinue
At the third occurrence	Stop 1 or 2 doses	Improved (< grade 3)	Continue infusion at 60% of original dose
		Not recovered	Discontinue
At the fourth occurrence	Discontinue	--	--

^a Greater than or equal to Grade 3 is defined as severe or life-threatening

Management of Skin Toxicities

Proactive skin treatment including skin moisturizer, sunscreen (SPF > 15 UVA and UVB), topical steroid cream (not stronger than 1% hydrocortisone) and an oral antibiotic (e.g., doxycycline), as prescribed by the physician, may be useful in the management of skin toxicities. Patients may be advised to apply moisturizer and sunscreen to face, hands, feet, neck, back and chest every morning during treatment, and to apply the topical steroid to face, hands, feet, neck, back and chest every night. Treatment of skin reactions should be based on severity and may include a moisturizer, sunscreen (SPF > 15 UVA and UVB), and topical steroid cream (not stronger than 1% hydrocortisone) applied to affected areas, and/or oral antibiotics, as prescribed by the physician.

Pulmonary Toxicity

In the event of acute onset or worsening of pulmonary symptoms, consider withholding panitumumab. If Interstitial Lung Disease is confirmed, discontinue panitumumab.

For Toxicities other than Dermatologic or Pulmonary

Withhold panitumumab for any grade 3 or 4 panitumumab-related toxicity with the following exceptions:

- Panitumumab will only be withheld for symptomatic grade 3 or 4 hypomagnesemia and/or hypocalcemia that persists despite aggressive magnesium and/or calcium replacement
- Panitumumab will only be withheld for grade 3 or 4 nausea, diarrhea, or vomiting that persists despite maximum supportive care.

Diarrhea management (refer to the 9.4 for management)

Electrolytes

Subjects should be evaluated and managed as per local medical practice. If hypomagnesemia is present, replacement should be managed with either oral and/or parenteral replacement, according to

institutional practice and to the degree of hypomagnesemia present. It is recommended that the subject's serum magnesium level should be maintained within the normal range, as much as possible, during study treatment. It is important to assess and manage serum potassium and calcium (adjusted for albumin) in subjects who have concomitant hypomagnesemia. Subject's serum potassium and calcium parameters are recommended to be managed, as per local medical practice, and kept within the normal ranges, as much as possible, during study treatment.

Criteria for Re-treatment with Panitumumab

- For dermatologic toxicities (see [Table 8.11](#))
- For toxicities other than dermatologic: If panitumumab was withheld, administration may recommence once the adverse event has improved to \leq grade 1 or returned to baseline. The reason for dose change of panitumumab is to be recorded on each subject's CRF(s).

8.2 Regorafenib: This section applies to adverse events associated with regorafenib. For adverse events associated with panitumumab, please refer to Section 8.1 and for TAS-102, please refer to Section 8.3.

NOTE: This drug is standard of care and FDA approved and, therefore, these are suggested but not mandated.

Discontinue regorafenib for the following conditions:

- Any grade arterial thromboembolic event,
- GI or other perforation or fistula formation,
- Intra-abdominal abscess,
- Wound dehiscence requiring medical or surgical therapy,
- Severe or life-threatening hemorrhage.

Regorafenib Dose Modifications

Dose Modification Level	Regorafenib (Orally, daily, mg, days 1-21 of each 28 day cycle)		
Initial dose	160	120	80
-1	120	80	40
-2	80	40	discontinue
-3	40	discontinue	
-4	Discontinue		

→ → Use the NCI Common Terminology Criteria for Adverse Events (CTCAE) version 5.0* unless otherwise specified ← ←

CTCAE System/Organ/Class (SOC)	ADVERSE EVENT	ACTION**
BASED ON INTERVAL ADVERSE EVENT		
Skin and subcutaneous tissue disorder	Palmar-plantar erythrodysesthesia syndrome	
	Grade 1	Maintain current dose
	Grade 2	1 st occurrence: Hold until grade \leq 1, then resume at current dose. If there is no recovery after a 4-week delay, treatment with regorafenib will be permanently discontinued. 2 nd or 3 rd occurrence: Hold until grade \leq 1, then resume at one dose level lower. Dose re-escalation is permitted at the discretion of the investigator if subject has completed one cycle at reduced dose without recurrence of event. If there is no recovery after a 4-week delay, treatment with regorafenib will be permanently discontinued. 4 th occurrence: Discontinue
	Grade 3	1 st occurrence: Hold until grade \leq 1 for a minimum of 7 days then resume at two dose levels lower. Dose re-escalation is permitted at the discretion of the investigator if subject has completed one cycle at reduced dose without recurrence of event. If there is no recovery after a 4-week delay, treatment with regorafenib will be permanently discontinued. 2 nd occurrence: Discontinue
	Grade 4	Discontinue
Vascular disorder	Hypertension	
	Grade \leq 2 asymptomatic	Maintain current dose
	Grade 3 asymptomatic	Maintain current dose
	Grade 2 or 3 symptomatic	1 st occurrence: Hold until symptoms have resolve, then resume at one dose level lower. 2 nd occurrence: Discontinue
	Grade 4	Discontinue
Investigations	Alanine aminotransferase (ALT), and/or Aspartate aminotransferase (AST), and/or Blood bilirubin increased ^a	
	Grade \leq 2	Maintain current dose
	Grade 3	1 st or 2 nd occurrence: Hold until recovery to grade \leq 2, then resume at one dose level lower if potential benefit outweighs the risk of hepatotoxicity. 3 rd occurrence: Discontinue
	Grade 4	Discontinue
	Platelet count decreased	
	Grade 2	Maintain current dose.
	Grade 3	Hold until recovery to grade \leq 1, then resume at one dose level lower.
	Grade 4	Hold until recovery to grade \leq 1, then resume at two dose levels lower.

→ → Use the NCI Common Terminology Criteria for Adverse Events (CTCAE) version 5.0* unless otherwise specified ← ←

CTCAE System/Organ/Class (SOC)	ADVERSE EVENT	ACTION**
Gastrointestinal disorders	Neutrophil count decreased	
	Grade 2	Maintain current dose.
	Grade 3	Hold until recovery to grade ≤ 1 , then resume at one dose level lower.
	Grade 4	Hold until recovery to grade ≤ 1 , then resume at two dose levels lower. Discontinue after second occurrence.
	Febrile neutropenia	
	Grade 3	Hold until resolution of fever and neutropenia to grade ≤ 1 , then resume at two dose levels lower. Discontinue after second occurrence.
	Grade 4	Hold until resolution of fever and neutropenia to grade ≤ 1 , then resume at two dose levels lower. Discontinue after second occurrence.
	Diarrhea	
	Grade 1	Maintain current dose
	Grade 2	Hold until recovery to grade ≤ 1 , then resume at one dose level lower.
	Grade 3	1 st or 2 nd occurrence: Hold until recovery to grade ≤ 1 , then resume at one dose level lower. 3 rd occurrence: Discontinue
	Grade 4	1 st occurrence: Discontinue or hold until recovery to grade ≤ 1 , then resume at two dose levels lower. 2 nd occurrence: Discontinue
	Mucositis oral	
	Grade 1	Maintain current dose
	Grade 2	Hold until recovery to grade ≤ 1 , then resume at one dose level lower.
	Grade 3	1 st or 2 nd occurrence: Hold until recovery to grade ≤ 1 , then resume at one dose level lower. 3 rd occurrence: Discontinue
	Grade 4	1 st occurrence: Discontinue or hold until recovery to grade ≤ 1 , then resume at two dose levels lower. 2 nd occurrence: Discontinue
	Small intestinal or colonic obstruction	
	Grade 2	Hold regorafenib for partial obstruction requiring medical intervention. Resume all study drugs at current dose when obstruction is resolved to grade ≤ 1 .
	Grade 3 or 4	Hold for all study drugs for complete obstruction. If surgery is necessary, subject may resume all study drugs at current doses after full recovery from surgery with permission of Principal Investigator.
General disorders and administration site conditions	Fatigue	
	Grade 1	Maintain current dose
	Grade 2	Hold until recovery to grade ≤ 1 , then resume at one dose level lower.

→ → Use the NCI Common Terminology Criteria for Adverse Events (CTCAE) version 5.0* unless otherwise specified ← ←

CTCAE System/Organ/Class (SOC)	ADVERSE EVENT	ACTION**
	Grade 3	1 st or 2 nd occurrence: Hold until recovery to grade ≤ 1, then resume at one dose level lower. 3 rd occurrence: Discontinue
	Grade 4	1 st occurrence: Discontinue or hold until recovery to grade ≤ 1, then resume at two dose levels lower. 2 nd occurrence: Discontinue

^a Discontinue regorafenib for the following:

- Any occurrence of AST or ALT more than 20 times the upper limit of normal (ULN).
- Any occurrence of AST or ALT more than 3 times ULN with concurrent bilirubin more than 2 times ULN.
- Re-occurrence of AST or ALT more than 5 times ULN despite dose reduction.

* Located at [REDACTED]

** Use the following to describe actions in the Action column:

- Omit = Treatment is not given for this cycle
- Hold/Delay = Treatment can be made up as part of this cycle
- Discontinue = Treatment is totally stopped

8.3 TAS-102: This section applies to adverse events associated with TAS-102. For adverse events associated with panitumumab, please refer to Section 8.1 and for regorafenib, please refer to Section 8.2.

NOTE: This drug is standard of care and FDA approved and, therefore, these are suggested but not mandated.

Complete blood cell counts prior to day 1 and on day 15 of each cycle are recommended. A maximum of 3 dose reductions are permitted to a minimum dose of 20 mg/m² twice daily. Do not escalate TAS-102 dose after it has been reduced.

→ → Use the NCI Common Terminology Criteria for Adverse Events (CTCAE) version 5.0* unless otherwise specified ← ←

CTCAE System/Organ/Class (SOC)	ADVERSE EVENT	ACTION**
BASED ON INTERVAL ADVERSE EVENT		
Hematologic	Neutrophil count decreased at cycle start	
	Grade 2-3	Delay treatment until ANC is ≥ 1500/mm ³ , then resume at same dose.
	Grade 4	Delay treatment until ANC is ≥ 1500/mm ³ . If recovery ≤ 1 week, resume at same dose. If recovery > 1 week, resume at 5mg/m ² /dose lower than previous dose.
	Neutrophil count decreased during cycle	
	Grade 4	Withhold treatment until ANC is ≥ 1500/mm ³ . If recovery ≤ 1 week, resume at same dose. If recovery > 1 week, resume at 5mg/m ² /dose lower than previous dose.

→ → Use the NCI Common Terminology Criteria for Adverse Events (CTCAE) version 5.0* unless otherwise specified ← ←

CTCAE System/Organ/Class (SOC)	ADVERSE EVENT	ACTION**
	Febrile neutropenia at cycle start	
	Grade 3	Delay treatment until ANC is $\geq 1500/\text{mm}^3$ and fever is resolved. After recovery, resume at $5\text{mg}/\text{m}^2/\text{dose}$ lower than previous dose.
	Febrile neutropenia during cycle	
	Grade 3	Withhold treatment until ANC is $\geq 1500/\text{mm}^3$ and fever is resolved. After recovery, resume at $5\text{mg}/\text{m}^2/\text{dose}$ lower than previous dose.
	Platelet count decreased at cycle start	
	Grade 2-3	Delay treatment until platelet count is $\geq 75,000/\text{mm}^3$. After recovery, resume at same dose.
	Grade 4	Delay treatment until platelet count is $\geq 75,000/\text{mm}^3$. If recovery ≤ 1 week, resume at same dose. If recovery > 1 week resume at $5\text{mg}/\text{m}^2/\text{dose}$ lower than previous dose.
	Platelet count decreased during cycle	
	Grade 2-3	Withhold treatment until platelet count is $\geq 75,000/\text{mm}^3$. After recovery, resume at same dose.
	Grade 4	Withhold treatment until platelet count is $\geq 75,000/\text{mm}^3$. If recovery ≤ 1 week, resume at same dose. If recovery > 1 week resume at $5\text{mg}/\text{m}^2/\text{dose}$ lower than previous dose.
General Disorders and administration site conditions	Fatigue	
	Grade 3	Delay until resolved to grade ≤ 1 . Resume at $5\text{mg}/\text{m}^2/\text{dose}$ lower than previous dose.
	Grade 4	Discontinue ^a
Gastrointestinal disorders	Mucositis oral	
	Grade 3	Delay until resolved to grade ≤ 1 . Resume at $5\text{mg}/\text{m}^2/\text{dose}$ lower than previous dose.
	Grade 4	Discontinue ^a

^a For all Grade 3 or 4 AEs except for Grade 3 nausea and/or vomiting controlled by antiemetic therapy or Grade 3 diarrhea responsive to antidiarrheal medication.

* Located at [REDACTED]

** Use the following to describe actions in the Action column:

- Omit = Treatment is not given for this cycle
- Hold/Delay = Treatment can be made up as part of this cycle
- Discontinue = Treatment is totally stopped

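### Section 8.1 lets panitumumab restart after a grade 3-4 infusion reaction resolves, 15.14 says to discontinue, and the protocol does not say which governs

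*Combined protocol and SAP*

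**What the plan says.** Section 8.0 tells sites that patients with drug-related adverse events "may require dose modification(s) as described in Sections 8.1, 8.2, and 8.3". For supportive care it adds: "Suggested supportive care measures for the management of adverse events are outlined in Section 9.0".

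In 8.1, the rule for toxicities that are neither dermatologic nor pulmonary is: "Withhold panitumumab for any grade 3 or 4 panitumumab-related toxicity with the following exceptions". There are two exceptions. One is low magnesium or calcium; the other is nausea, diarrhea or vomiting. The re-treatment criteria at the end of 8.1 allow a withheld drug to restart once a non-dermatologic event is at grade 1 or less or back to baseline.

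Infusion reactions are dealt with only in Section 15. Section 15.14 (Administration) halves the infusion rate for grades 1-2 and says to discontinue for grades 3-4. Section 15.19b2 (Nursing Guidelines) says to stop the infusion, inform the physician and treat, and that premedication may be needed before later infusions. It gives no grade. Section 8.1 does not cite 15.14, and 15.14 does not cite Section 8.

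**The concern.** A patient with a grade 3-4 infusion reaction that resolves is covered by two instructions with different consequences. Under 8.1 the drug was withheld and may be given again. Under 15.14 it is discontinued. The section that sites are sent to for dose modification is the more permissive one.

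What is at stake is the safety of the individual patient, namely re-exposure after a severe or life-threatening reaction, and consistent handling across sites. The estimate of treatment effect is not at stake.

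**Working it through.** The plan gives no figure to reproduce. The check is a comparison of texts, followed by a rough look at frequency.

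**1. The texts side by side, for a grade 3-4 infusion reaction**

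| Text | Immediate action | Later dosing |
|---|---|---|
| 8.1, general rule | Withhold | Restart permitted at grade 1 or less, or baseline |
| 15.14 | Discontinue | Not stated whether this means the infusion or the drug |
| 15.19b2 | Stop the infusion and treat | Later infusions envisaged, no grade limit |

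**2. Does the 8.1 rule reach infusion reactions?** Yes. Section 15.17 lists infusion related reaction as a procedural complication, so it is neither dermatologic nor pulmonary, and neither exception covers it.

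**3. Do the two verbs differ?** Probably. The key in 8.1 reads "Discontinue = Treatment is totally stopped", as distinct from a hold or delay. Section 8.1 also keeps the stronger verb for particular events: "If Interstitial Lung Disease is confirmed, discontinue panitumumab". The support is limited, though. The key is introduced by "Use the following to describe actions in the Action column", the panitumumab part of 8.1 has no such column, and the same key is repeated in 8.2 and 8.3.

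**4. Where would a site look?** Section 8.0 points to 8.1-8.3 and to Section 9.0. Section 9.0 does not mention infusion reactions. Section 8.1 sends the reader to 9.4 for diarrhea but gives no pointer to 15.14.

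**5. How often could this arise?** Panitumumab patients: n = 53 (evaluable per arm, 16.15) to 120/2 = 60 (half of maximum accrual, 16.2).

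- Infusion related reaction, listed below 1%, any grade. At 1%: 53 × 0.01 = 0.53 to 60 × 0.01 = 0.60 patients.
- Hypersensitivity, listed at 1-10%, any grade: 53 × 0.01 = 0.53 to 60 × 0.10 = 6.0 patients. The documents do not say how many of these events would occur at infusion.
- Re-exposure needs two further shares that the documents do not give: the grade 3-4 share s and the share rechallenged q. With a 1% rate, p = 0.01 × s × q, the expected number is n × p, and the chance of at least one is 1 − (1 − p)^n.
  - Assuming s = q = 10%: p = 0.0001, expected 0.0053-0.0060, chance 0.5-0.6%.
  - Assuming s = q = 50%: p = 0.0025, expected 0.13-0.15, chance 12-14%.

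The last two lines are illustrations on assumed shares and a rate that may not capture all relevant events.

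**6. Effect on the primary analysis.** Under 13.3, patients who leave protocol treatment for any reason are followed for survival. Under 16.13, an eligible, consented, randomized patient who received any protocol treatment is evaluable. A patient stopped after a reaction therefore still contributes to OS.

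**The case against.** The strongest reply is that the texts can be applied together. The restart criterion applies only if the drug was withheld, and a drug discontinued under 15.14 was not merely withheld. Section 15.14 is the specific rule, it sits where administration instructions belong, and a site reading the whole protocol will find it. Restart under 8.1 is optional, and 8.0 says "dose modifications are permitted outside of those provided in the protocol" when the investigator judges this to be in the interest of patient safety. Serious reactions also fall under the expedited reporting rules in Section 10. The deadlines (24 hours for grade 4, 7 days for grade 3) would normally pass before the next dose, because dosing is on Days 1 and 15.

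Most of this stands as mitigation. It does not settle the matter. The protocol gives no order of precedence, and 15.19b2 is just as specific to infusion reactions yet leaves later dosing open. Discretion permits stopping without requiring it, and reporting does not forbid rechallenge.

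A reader might go further and infer that 15.14 plainly forbids rechallenge, so that the protocol flatly contradicts itself. The documents do not support that. The instruction follows directly on one about infusion rate, so *discontinue* could mean ending that infusion only. On that reading there is no contradiction, but then no text clearly requires a permanent stop.

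**Conclusion.** The point holds as an unresolved inconsistency: a site using 8.1 as written may rechallenge after a severe infusion reaction, and nothing in the protocol says whether 15.14 overrides it. It is a minor safety clarification, held with moderate confidence because the meaning of 15.14 is open.

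The event is uncommon, but its frequency in this trial cannot be bounded from the documents. A reader might take 0.53-0.60 patients as a ceiling. It is not one, because it rests on a single listed term and hypersensitivity is listed separately at up to 10%. Exclusion 3.29o removes patients with known hypersensitivity to the study drugs but exempts cetuximab, and the documents do not say how that changes the risk.

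A reader might also think the re-treatment criteria need a carve-out for interstitial lung disease. They do not, because 8.1 already says to discontinue for that event. OS and power are unaffected.

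**What to change.** 1. In 8.1, add: *Grade 3 or 4 infusion reaction: permanently discontinue panitumumab; no re-treatment (see 15.14).*
2. In 15.14, write *permanently discontinue panitumumab* for grade 3-4 infusion reactions. This settles the open reading in the stricter direction.
3. In 15.19b2, limit the sentence on later infusions to grade 1-2 reactions.

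The cost is one wording amendment in three places, with no new data, visits or patients. The downside is that, rarely, a patient stops panitumumab who might otherwise have been rechallenged. That patient is still followed for survival under 13.3.

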9.6 Hypomagnesemia: Panitumumab should be held for severe and/or life threatening hypomagnesemia. Consider IV replacement and magnesium oxide 400 mg PO BID.

9.7 Panitumumab-related skin rash. The treating physician may elect to preemptively treat subjects receiving panitumumab to mitigate or prevent skin toxicities. Doxycycline 100mg every 12 hours or equivalent, emollient, and hydrocortisone 1% cream is recommended, but not required for skin rash prophylaxis (Refer to Section 8.1)

9.8 Hypertension: Early and aggressive medical management of hypertension is strongly recommended to minimize the need for dose holding and/or dose reductions. Addition or adjustment of blood pressure medications should be considered for blood pressure values persistently $> 140/90$. Symptomatic or asymptomatic patients with poorly controlled blood pressure ($> 150/100$ on 3 measurements over 2 weeks) for over one month (despite the addition and

adjustment of anti-hypertensive therapy) should have regorafenib held until their blood pressure is $\leq 140/90$.

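### Sections 8.1 and 9.6 give different criteria for holding panitumumab in hypomagnesemia, and no text says which is the default

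*Combined protocol and SAP*

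**What the plan says.** Section 8.1 covers panitumumab toxicities other than dermatologic or pulmonary. Its general rule is "Withhold panitumumab for any grade 3 or 4 panitumumab-related toxicity with the following exceptions". One exception is for electrolytes: "Panitumumab will only be withheld for symptomatic grade 3 or 4 hypomagnesemia and/or hypocalcemia that persists despite aggressive magnesium and/or calcium replacement". The Electrolytes paragraph adds "Subjects should be evaluated and managed as per local medical practice" and recommends keeping magnesium in the normal range as far as possible. After a hold for a non-dermatologic toxicity, Section 8.1 allows treatment to restart once the event is grade 1 or lower, or back to baseline.

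Section 9.6, in the supportive-care chapter, says "Panitumumab should be held for severe and/or life threatening hypomagnesemia" and then advises considering replacement. It assigns no CTCAE grade.

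Section 8.0 describes the roles of the two chapters. Subjects with drug-related events "may require dose modification(s) as described in Sections 8.1, 8.2, and 8.3". For Section 9.0 it says "Suggested supportive care measures for the management of adverse events are outlined in Section 9.0". It also says "At the discretion of the Investigator, dose modifications are permitted outside of those provided in the protocol" where the investigator judges this to be in the interest of the subject's safety.

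On monitoring, Section 15.19b4 asks for a magnesium level before every panitumumab infusion. The magnesium row in Section 4.0 has a test within 7 days before randomization but no entry in the baseline column. Footnote 8 makes the Day 15 visit optional from cycle 7.

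**The concern.** Both passages instruct the site when to hold the same drug for the same toxicity, and they do not name the same events. Section 8.1 carves hypomagnesemia out of the general grade 3 or 4 rule unless further conditions are met. Section 9.6 states a hold without those conditions.

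The toxicity is not rare: Section 15.17 lists hypomagnesemia among panitumumab effects seen in more than 10% of patients. For the same laboratory result, one site could continue infusions with replacement under Section 8.1. Another could hold under Section 9.6 and then wait for the Section 8.1 restart criterion. That is an ambiguity about patient safety and consistent treatment in the experimental arm.

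**Working it through.** No plan figure is in question, so the check is a comparison of text.

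**Step 1. Conditions in each section.**
- Section 8.1: the word *only* makes three conditions jointly necessary, namely grade 3 or 4, symptomatic, and persisting despite aggressive replacement.
- Section 9.6: one condition, that the event is severe and/or life-threatening. Replacement is something to consider alongside the hold, not a step that must fail first.

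**Step 2. Putting Section 9.6 on a grade scale.** Section 9.6 gives no grade. The only mapping in the panitumumab section is footnote a of Table 8.11: "Greater than or equal to Grade 3 is defined as severe or life-threatening". That footnote belongs to a table of skin symptoms, so applying it to magnesium is an inference. On that reading:

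| Hypomagnesemia event | Section 8.1 | Section 9.6 | Agree? |
|---|---|---|---|
| Grade 1 or 2 | no hold | no hold | yes |
| Grade 3 or 4, symptomatic, persists despite aggressive replacement | hold | hold | yes |
| Grade 3 or 4, asymptomatic | no hold | hold | **no** |
| Grade 3 or 4, symptomatic, replacement untried or working | no hold | hold | **no** |

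**Step 3. Does the conflict depend on the inference?** Its extent does; its existence does not. Suppose Section 9.6 is read narrowly, so that only life-threatening events are certain to be covered. A life-threatening event that has not yet been treated, or that is responding to replacement, is held under Section 9.6 and not under Section 8.1. The conflict disappears only if the Section 9.6 wording already means symptomatic and refractory to replacement, and no text says that.

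**Step 4. Is there a precedence rule?**
- Section 8.0 assigns dose modification to Sections 8.1 to 8.3 and describes Section 9.0 as suggested supportive care. This favors 8.1.
- Sections 8.2 and 8.3 carry a note that their modifications are suggestions rather than mandates. Section 8.1 has no such note, which also favors 8.1.
- Section 8.1 points to 9.4 for diarrhea, and 9.7 points back to 8.1 for rash. On hypomagnesemia neither 8.1 nor 9.6 points to the other.
- No sentence ranks the two.

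**Step 5. Monitoring schedule (separate and minor).** Screening magnesium may be up to 7 days before randomization, and Section 6.16 allows treatment to start up to 7 days after it. The last value scheduled in Section 4.0 can therefore be 7 + 7 = 14 days old at Cycle 1 Day 1. CBC and chemistry have a baseline entry to cover this; magnesium does not. From cycle 7 the Day 15 visit may be dropped, while Sections 7.1 and 7.5 keep the Day 15 infusion in each cycle.

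**The case against.** The strongest reply is that the structure of the protocol already settles the matter. Section 8.1 is the dose-modification section, it is specific and exclusive, and it is written as a deliberate exception. Section 9.6 is a short note using *should*, in a chapter labelled as suggested. A reader might infer that 8.1 therefore prevails. The lean is real, but Section 9.6 is itself a hold instruction, and nothing tells a site to disregard it.

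A second reply is that Section 8.0 lets investigators depart from the listed modifications for safety, so a site that holds is not in breach. That stands, and it limits the consequence. It does not identify the default from which the investigator would be departing. The Electrolytes paragraph likewise governs evaluation and replacement, not the hold criterion.

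A third reply is that the wider conflict in the table rests on a skin footnote. That is correct, and the narrower version of the conflict should be taken as the firm one.

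On the monitoring schedule, Section 15.19b4 already asks for a value before each infusion, and footnote 8 permits additional laboratory studies. A site that follows 15.19b4 will not rely on a 14-day-old value. What remains is a mismatch between the schedule and the nursing text.

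**Conclusion.** The inconsistency is real and worth correcting. It is certain for life-threatening events that are untreated or responding to replacement. It extends to asymptomatic grade 3 or 4 events, and to symptomatic ones where replacement is untried or working, if severe or life-threatening means grade 3 or higher. The consequence is possible variation between sites in holding panitumumab, reduced but not removed by the lean toward 8.1 and by investigator discretion.

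Its frequency cannot be estimated from the documents. Section 15.17 lists hypomagnesemia above 10% and decreased blood magnesium at 1% to 10%, both without grades, and nothing gives the split by symptoms or response to replacement. A reader might assume a grade 3 or 4 rate and compute the chance of at least one event among the 53 evaluable panitumumab patients. That would be the chance of any such event, not of a conflict. Nor is 53 a ceiling: maximum accrual is 120, so about 120 / 2 = 60 per arm.

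A reader might also infer an effect on the trial's conclusions. The documents do not support that. Overall survival runs from randomization to death, and the final analysis counts eligible randomized patients who received any protocol treatment, so a held dose removes nobody. The suspension rule in Section 16.4.2 counts related grade 4 or higher events and does not depend on whether a dose was held.

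**What to change.** The sponsor's clinicians should reconcile Sections 8.1 and 9.6 so that one hold criterion for hypomagnesemia, stated in CTCAE grades, appears consistently wherever it is mentioned. No view is taken on which criterion is right. Having one section simply defer to the other would itself choose a rule, so that too is a decision for the clinicians.

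As a separate minor edit, the Section 4.0 magnesium row and footnote 8 should be reconciled with Section 15.19b4, so that the schedule and the nursing guideline ask for the same tests.

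The cost is a wording change in two sections, a small edit to the test schedule and a memo to sites. No new visit is needed, because patients already attend for each infusion.
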